Patient demographics and clinical characteristics. Patient demographics and past medical history will be collected as part of the study (Appendix D). Patient demographic variables to be collected include age, race, education level, marital status, and employment status. Specific confounding variables associated with the type of intervention and outcome will be collected including patients' preferred learning style, comfort level with technology, and anxiety. Preferred learning style will be assessed using the three styles of learning reading, seeing, doing, or listening (Bastable, 2008). Comfort level with technology will be assessed using a five-point Likert scale with zero being, "not comfortable at all" and five being "very comfortable." Anxiety associated with anticipated pain will be assessed on ten-point. Relevant past medical and surgical history will also be collected including past major orthopedic surgeries, chronic pain, preoperative use of opioids, and mental health conditions. The patient demographic collection form will be administered using paper and pencil survey. The patient will be given the form when they arrive to the ambulatory orthopedic clinic for their perioperative visit, one to two days prior to their scheduled surgery. It will take participants approximately five minutes to complete the survey.

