Chart audits. Chart audits of the electronic health record will be conducted after discharge to collect the remaining clinical data. Data to be collected will include total opioid requirements as indicated by the medication administration record; primary surgical procedure as reported in the surgical listing and the operative report; type of regional anesthesia as indicated in the anesthesia record; length of stay; and discharge disposition as reported in the hospital dismissal summary. Additionally, the past medical history will be reviewed to confirm patient reported history of chronic pain, preoperative use of opioids, and mental health conditions. The researcher and a staff RN will conduct these chart audits.

Limitations

The design of this study does present some limitations. Participants in the study group will receive enhanced pain content that is delivered using an alternative method, ultimately testing both the delivery method and the content. The duality of the study intervention is a confounding variable and may make differentiating

the cause of the outcome difficult. Another limitation is that preoperative educational classes are available to patients to attend if they choose. All patients receive the same pamphlets and information in the mail when surgery is scheduled. An in-person didactic class is optional for patients. Some pain education is offered in this class. Currently only 49% of patients attend these classes. It is anticipated that some patients enrolled in the study will have received varying levels of education prior to their hospital admission. This is an antecedent variable that will be collected as part of the chart audit and accounted in the data analysis. The two nursing units involved in the study are located within the same hospital. It is possible that nursing staff from the intervention unit may float to the control unit and educate study patients using content from the expanded education from the intervention on the iPads. Pre-testing knowledge of pain and measured again at the end of the intervention (prepost) using a paired t-test analysis will strengthen the design of the study. Only opioid use for pain control is being measured.

Data Management

Data Collection Procedure

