Data will be collected at three points in time using paper and pencil survey's and chart audits. The data collection protocol can be found in Appendix G. After completion of the HIPAA form, demographic and past medical history information and pain knowledge survey will be administered in the ambulatory clinic at the time of the perioperative surgical visit. A paper and pencil survey/form will be provided to the patient when they arrive in the clinic for their perioperative appointment and returned to the desk staff when completed.

The intervention will occur on the postoperative inpatient care unit (PCU) starting at the time the patient arrives on the unit from the post anesthesia care unit (PACU). The intervention will continue through the course of care until discharge. At the time of discharge the patient will complete the Revised American Pain Society Patient Outcomes Questionnaire (APS-POQ-R) (Gordon et al., 2010) and the revised knowledge-based Patient Pain Questionnaire (PPQ) (Ferrell & Rivera, 1997; Reynolds, 2009). The use of these two widely used instruments will ensure that the information being collected is highly reliable and valid, truly measuring what the study is seeking to evaluate. These paper and pencil survey's will be provided to the patient prior to discharge and collected from the patient by the staff registered nurse (RN) and/or charge nurse. In addition to training and education on the intervention, staff will receive direction on the data (survey) collection process and requirements. The administration of the post-intervention surveys at the point of care, before the patient has left the study environment, will help to prevent the loss of study participants due to non-response or failure to complete follow-up surveys.

After discharge the researcher will conduct a chart review to collect clinical data including opioid consumption totals, past medical history, anesthesia type, and length of stay. The researcher in addition to one RN will be responsible for chart audit data collection. The RNs will be trained by the researcher on chart audit processes. The RNs will complete the institutions IRB education requirements for staff assisting with research data. A tentative timeline has been developed as a GNATT chart in Appendix H. All collected data from the paper surveys' and chart audits will be entered in to SPSS for analysis. Data storage and management is discussed further under ethical considerations.

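### The plan promises to account for preoperative class attendance, but the between-arm analysis is an unadjusted t-test and no described collection list names the item

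*Combined protocol and SAP*

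**What the plan says.** The Limitations section explains that all patients get the same mailed material, but that an in-person class with some pain education is optional: "Currently only 49% of patients attend these classes". On the resulting differences in prior education it says: "This is an antecedent variable that will be collected as part of the chart audit and accounted in the data analysis". That sentence makes two commitments, one on collection and one on analysis.

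**Collection.** Three places describe what will be gathered.
- Chart audits (under Instruments) begins "Data to be collected will include total opioid requirements as indicated by the medication administration record", continues with surgical procedure and regional anesthesia, and ends with "length of stay; and discharge disposition as reported in the hospital dismissal summary". It then adds confirmation of the reported medical history.
- Data Collection Procedure says the researcher will "collect clinical data including opioid consumption totals, past medical history, anesthesia type, and length of stay".
- Patient demographics and clinical characteristics describes the intake form: "Patient demographic variables to be collected include age, race, education level, marital status, and employment status"; confounders that "will be collected including patients' preferred learning style, comfort level with technology, and anxiety"; and history "including past major orthopedic surgeries, chronic pain, preoperative use of opioids, and mental health conditions".

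None of the three names the class or prior pain education. Education level on the intake form is a demographic item.

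**Analysis.** The Data Analysis Plan compares the two groups by an independent t-test, with nonparametric tests if normality fails. It also says that baseline differences will be examined to find characteristics needing control, but it names no variable and no adjusted model.

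**The concern.** The class teaches pain content before the intervention begins, so it overlaps with what the iPad program teaches and with what the knowledge questionnaire measures. About half of patients attend. Arms follow the unit on which the patient is bedded, with bed availability playing a part, and not a patient-level randomization list, so balance in attendance is not guaranteed.

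The authors saw this and gave their answer in Limitations. An independent t-test has no place for a covariate, however, so even a complete record of attendance would not enter the comparison. The baseline check does not close the gap: adjustment would depend on whether attendance happened to look different between arms, and no threshold or model is given. If the item were also missed at abstraction, an imbalance could be neither seen nor corrected.

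**Working it through.** **1. The plan's own figure.** Sample Size gives d = 0.50, power 0.80, alpha 0.05 and 64 per arm. An exact two-sided two-sample t-test needs 63.77 per arm, which rounds up to 64 (the plan does not state sidedness; two-sided is assumed). The figure reproduces, and 64 per arm is used below.

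**2. Promise against procedure.**

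| Place | Class attendance named? | Adjustment stated? |
|---|---|---|
| Limitations | Yes, source is the chart audit | Yes, in general terms |
| Chart audits | No | – |
| Data Collection Procedure | No | – |
| Intake-form description | No | – |
| Data Analysis Plan | No | Unadjusted t-test; generic control of observed differences |

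The paired t-test mentioned in Limitations compares knowledge before and after within patients. It does not compare arms and does not adjust for the class.

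**3. Chance imbalance in attendance.** Inputs: attendance p = 0.49 (Limitations), n = 64 per arm (Sample Size), allocation treated as random.

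- SE of the difference = sqrt(2 × 0.49 × 0.51 / 64) = 0.0884, or 8.8 percentage points.
- Gap of at least 10 points: z = 0.10 / 0.0884 = 1.13, two-sided probability 0.26.
- Gap of at least 15 points: z = 0.15 / 0.0884 = 1.70, probability 0.09.
- Gap of at least 30 points: z = 0.30 / 0.0884 = 3.39, probability about 0.0007.

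**4. Bias from a given gap.** The documents give no effect of attendance on any outcome. Assume 0.3 to 0.5 SD. Bias in SD units = gap × effect.

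- 15 points: 0.15 × 0.3 = 0.045 and 0.15 × 0.5 = 0.075, or about 0.05 to 0.08 SD.
- Against the design effect: 0.045 / 0.50 = 9% and 0.075 / 0.50 = 15%.

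**5. Rejection rate given that gap and no true effect.** Noncentrality = bias × sqrt(64 / 2), with 126 degrees of freedom.

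- Bias 0.045: noncentrality 0.25, rejection rate 5.7%.
- Bias 0.075: noncentrality 0.42, rejection rate 7.1%.

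These rates are conditional on a 15-point gap. Averaged over random allocations, where gaps fall in either direction, the t-test keeps an error rate near 5%.

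**The case against.** The strongest reply is that the sentence in Limitations is itself a collection instruction. It names the chart audit as the source and follows shortly after the Chart audits paragraph. The lists are also open in wording. The one in Data Collection Procedure omits surgical procedure and discharge disposition, which Chart audits includes, so it is plainly a summary. The Variables section places the full account of data points in a code book and refers to Appendix B; the form is in Appendix D and the collection protocol in Appendix G. None of these could be seen, and staff are trained on the audit. Absence from the intake form contradicts nothing, because the stated source is the chart.

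All of that stands. A reader might infer from the lists that staff who follow the procedures will not have this variable. The documents do not support that; they support only that the described procedures do not name it and that it may be missed.

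A second reply is that the problem is partly handled. Baseline knowledge is measured at the preoperative visit and would reflect class learning if the class came first, and the plan commits to examining baseline differences. This stands in part. The stated between-arm test does not use the baseline score, that score does not cover pain, participation or opioid use, and controlling only what looks different is weaker than the promise in Limitations.

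A third reply is that the consequence is small. It is, under chance allocation. A reader might also infer a badly inflated error rate: a 30-point gap with a 0.5 SD effect would give 0.15 SD of bias and about 13% rejection. But such a gap has a chance probability of about 0.0007. It would need systematic differences in bed placement, and the documents give no evidence of these for attendance; they describe an even split between units and researchers blinded until bed assignment.

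**Conclusion.** The point holds for the analysis and, more weakly, for collection. The plan commits to accounting for prior education and then specifies a between-arm test that cannot do so. The collection half is a risk of omission, to be settled by looking at Appendix G and the code book.

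The matter is minor in size. By chance alone, a gap of 15 points or more occurs in 9% of trials of this size, and a gap of 15 points moves the comparison by about 0.05 to 0.08 SD against a design effect of 0.50. This rests on 49% attendance applying to enrolled patients, 64 analyzed per arm, and an assumed attendance effect of 0.3 to 0.5 SD. Larger bias would require placement on the two units to be related to attendance. Adjusting for attendance would not remove other differences between the units.

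**What to change.** 1. **Data Analysis Plan.** For each between-arm comparison, replace the independent t-test with a linear model (ANCOVA) containing arm and class attendance (yes/no). Prespecify attendance as a fixed covariate, kept whether or not it looks imbalanced. If the nonparametric fallback stays, state its adjusted counterpart.
2. **Chart audits and Data Collection Procedure.** Name class attendance, its record source and its coding, and confirm that Appendix G and the code book agree.
3. **Intake form.** Add one yes/no question on attending the in-person class. The form is completed one to two days before surgery, before the arm is known, so the answer cannot be affected by the intervention. It backs up the chart entry.

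Cost: one line on a form that takes about five minutes, one more SPSS variable, minor recall error, and one degree of freedom out of 126.

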
Study Design and Methods

Methods: *Describe, in detail, the research activities that will be conducted under this protocol:*

Variables

The independent variable is the type of patient education deliverable given to the two study arms, group A (experimental group, real-time, interactive, mobile education system) and group B (control group, standard of care). The dependent variables are 1) patient knowledge, 2) patient perceived participation in pain management, 3) high and low pain scores, and 4) total opioid consumption. A simple table of the independent, dependent, and additional variables are presented in Appendix B. A detailed accounting of all data points including variable type, theoretical definitions, and operational definitions can be found in the detailed code book.

Method

Design

This prospective study has been designed as quasi-experimental study. This study design was selected for several reasons. This study seeks to explore both a treatment and control group in efforts to compare outcomes which are dependent on the type of intervention. To control for fidelity of the intervention and avoid cross over, behavior changes from nurses providing the intervention, the intervention the patient receives will be determined by the location they are bedded in hospital. Orthopedic TJA patients are assigned at random and based on bed availability to one of two patient care units. One of the two patient care units will offer standard education the other unit will offer the mobile, iPad based education. The patient care unit to offer the mobile, iPad based education will be selected at random. This study design will help minimize will reduce the risk of selection bias, increase fidelity of the intervention, and increases the probability that the differences demonstrated between the study groups will be attributed to the actual intervention under study.

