Study participants will be assigned into one of two study arms, intervention or control, based on random assignment to the two designated units. At the time of consent, patients will be informed that there are two study arms and that some subjects will receive enhanced pain management education; however, subjects will not explicitly be informed if they are in the intervention or control arm of the study. Participants who have verbally consented will receive a HIPAA authorization form accompanied by a letter reminding them of the study and their consent to participate at the time of the preoperative visit. This typically occurs one to two days before surgery. Participants will be asked to sign the HIPAA authorization form and return the clinical staff. Participants will be provided an extra copy for their records. No Patient data will be collected prior to this. Once HIPAA has been signed participants will complete the intake survey provided with the packet of information.

Researchers are blinded to the study arm the participant was enrolled in until after consent has been obtained, the patient is enrolled in the study, and has been admitted to the hospital and assigned a bed. Once enrolled and consented, bed control will be notified to assign the patient(s) to one of the two designated patient care units with no specific direction offered on which unit the patient(s) should be assigned to. The only direction provided will be to split the patients evenly between the two units. Only ten study arm participants may be enrolled and active at one time. This is limited based on the number of available iPad devices for the purposes of this study.

Study Population

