Patients enrolled in the study arm will be given an iPad on admission to the post-surgical unit. The RN will instruct the patient on how to use the iPad and the program. The device will remain with the patient until discharge. The patient, independently or with the nurse, may use the program at any point during the inpatient care experience. The RN will use the iPad to engage patients in their pain management and care. Intervention fidelity will be monitored by requiring the RN to indicate when and how often they observed and/or directly engaged the patient in pain education using the mobile device. A checklist will be available on the patients chart for the RN to complete at the end of each shift through the duration of the patients hospital stay.

Control group. The control group will receive the current standard of care which consists of verbal instruction and pain management pamphlets. At a minimum, the patients will receive two educational pamphlets titled *Your Pain and Discomfort Management Menu* and *Communicating About Your Pain*. The pain management menu is designed to provide the patient with basic pain information with a focus on non-pharmacologic pain interventions. The pain communication pamphlet offers a more comprehensive explanation about pain, assessment of pain (0-10 scale), communicating with the healthcare providers, and pain management options. The content of these two documents is a portion of the education the study patients will receive using the mobile application. These two documents are existing educational material available through the Department of Patient Education. These educational materials were developed by the Department of Anesthesia and Pain Service in conjunction with the Department of Patient Education. Verbal instruction is inconsistent and is nurse dependent. At a minimum the nurse is instructed to provide the two pamphlets to the patient and follow-up with the patient to address any questions. Additional printed education materials are available through the department of patient education and verbal instruction may be tailored based on nursing assessment and patient need. It is important to note that all educational content available to the study participants is available to the control group in different forms or functions. Fidelity to standard of care will be

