monitored by requiring the RN to indicate when and how often they observed and/or directly engaged the patient in pain education using standard pamphlet educational material. A checklist will be available on the patients chart for the RN to complete at the end of each shift through the duration of the patients hospital stay.

Management of interventions and study participants. The implementation of the interventions in the study and control arm will be closely monitored by the researcher. Educational in-services for all shifts will be held on various days. Education will include the research protocol, goals of the study, use of the mobile iPad patient education in practice, and data collection procedures. To ensure all staff have access to the education, a brief video will be disseminated via e-mail to be viewed at staff convenience prior to the start of the study. Participants in the study will be denoted by a specific color coded label at the door. This will notify and flag direct care staff to ensure that the appropriate study protocol is followed. The research protocol for each arm of the study and instructions for the mobile education application will be placed in the research reference book, located at each nursing sub-station. For participants whom are enrolled in the study arm, the researcher will deliver the iPad either directly to the patient or to the bedside RN caring for the patient. The RN will receive one-on-one, just in time education at the point of device delivery. The researcher will also make daily rounds and random care observations with nurses caring for participants enrolled in the study. Additional education and reminders will be offered at the point of care and as needed.

Instruments

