Pain outcomes. The Revised American Pain Society Patient Outcome Questionnaire (APS-POQ-R) will be used to evaluate the patients' perception of their pain management experience and outcomes (Appendix E). The APS-POQ-R is a 23-item, two-page questionnaire measuring five subscales of the patient experience and one aspect measuring non-pharmacologic management. These 6 aspects include (1) pain severity and relief; (2) impact of pain on activity, sleep, and negative emotions; (3) side effects of treatment; (4) helpfulness of information about pain treatment; (5) ability to participate in pain treatment decisions; and (6) use of nonpharmacological strategies (Gordon, Polomano, Pellino et al., 2010). There are 14 symptom-based questions to indicate symptom severity using a ten-point scale (0-10). The higher the score, the more severe the symptom experience. Two additional symptom-based questions explore severity of pain over time and pain relief using a ten-point scale with a range of 0% to 100%. For pain severity over time, a higher score indicates a higher incidence of severe pain in 24 hours. For pain relief, a higher score indicates a more positive response to pain relief. These data points will help determine the effectiveness of the intervention on pain outcomes (pain scores). Three questions are associated with the pain education experience. Using a ten-point scale (0-10), the higher response scores indicate a more positive experience rating. Pain experience here is assessed by

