generalized satisfaction with pain relief and participation in treatment decisions. These data points will help determine the influence of pain education on satisfaction with educational material/delivery and participation. The reported participation score will be used to measure the degree to which the patient is engaged by a means of active participation in care and treatment. The remainder of the survey questions use a single word association to answer the question rather than a measurable scale. The APS-POQ-R has demonstrated adequate psychometrics, construct validity, reliability, and clinical feasibility. Internal consistency reliability was acceptable with a Cronbach α of 0.86. The individual subscales were also assessed for reliability with the resulting Cronbach α as follows affective subscale, $\alpha = 0.82$; pain severity and sleep interference subscale, $\alpha = 0.83$; perceptions of pain care subscale, $\alpha = 0.70$; interference with activity, $\alpha = 0.82$; and adverse effects subscale, $\alpha = 0.63$ (Gordon, Polomano, Pellino et al., 2010). This tool is open source and available for application without further permission (Gordon, Polomano, Pellino et al., 2010).

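### Discharge ratings are handed back to the unit nursing teams that deliver the education, with no confidential return described, so a between-unit reporting difference could not be told apart from the arm effect

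*Combined protocol and SAP*

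**What the plan says.** **Collection.** Under Data Collection Procedure, and again at the end of the Pain knowledge paragraphs in Instruments, the discharge forms are "collected from the patient by the staff registered nurse (RN) and/or charge nurse". The stated reason for collecting them before the patient leaves is to limit non-response.

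**Who delivers the education.** On the iPad unit, "The RN will use the iPad to engage patients in their pain management and care". On the control unit, "At a minimum the nurse is instructed to provide the two pamphlets to the patient". Under Design, "One of the two patient care units will offer standard education the other unit will offer the mobile, iPad based education".

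**What the nurses know.** Management of interventions and study participants describes in-services for staff: "Education will include the research protocol, goals of the study, use of the mobile iPad patient education in practice, and data collection procedures". Participants are also marked by a coloured label at the door.

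**What is rated.** The Pain outcomes paragraphs describe three 0-10 items on the education experience, for which "the higher response scores indicate a more positive experience rating". They add: "The reported participation score will be used to measure the degree to which the patient is engaged". Perceived participation is one of the four dependent variables under Variables, and it appears in the hypothesis.

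**What the patients know.** At consent, "subjects will not explicitly be informed if they are in the intervention or control arm of the study".

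The Limitations section does not mention nurse collection of the forms.

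**The concern.** A patient who rates pain care and participation, and returns the form to the team that gave that care, may rate generously. If the two teams differ in how far this happens, the difference appears as a difference between arms. A gap is plausible: nurses on the iPad unit are presenting a new tool and know what the study hopes to show. At stake is the interpretation of participation and of the pain-experience aim, both of which rest on this one self-completed form. The problem cannot be repaired after the forms are in.

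**Working it through.** **1. The plan's own figure.** Sample Size gives d = 0.50, power 0.80, alpha 0.05 and 64 per arm. Sidedness is not stated.
- Normal approximation, two-sided: n = 2(1.960 + 0.842)² / 0.50² = 62.8, so 63.
- Two-sample t-test, two-sided: 63.77, so 64, with power 80.1%.
- One-sided t-test: 50.15, so 51.

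The plan's 64 is reproduced by the two-sided t-test, which is used below. This point does not change the sample size.

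**2. What the t-test estimates.** Let δ be the true education effect, and let c_A and c_B be the mean reporting shifts on the iPad and control units. The expected difference in means is

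δ + (c_A − c_B).

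If c_A = c_B, the shift drops out, apart from any compression at the top of a 0-10 scale. If the two differ, the data identify only the sum. Unit and arm coincide, so no unit term can be fitted alongside arm.

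**3. Could a baseline score help?** Instruments has both surveys completed at the start of the study as well as at discharge. Data Collection Procedure lists only the knowledge survey at the preoperative visit. On either reading, a preoperative form cannot rate inpatient care that has not yet been given, so it cannot capture the discharge reporting shift.

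**4. Size, by assumption.** The documents give no value for c_A − c_B. Write it as b standard deviations, with equal SDs, 64 per arm and no dropout. The test has 126 degrees of freedom, and the noncentrality is b√(64/2) = 5.657b. An observed difference of about 0.35 SD is enough for p < 0.05.

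No true effect, shift of b SD in either direction:

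| b (SD) | Noncentrality | Share of d = 0.50 | Rejection |
|---|---|---|---|
| 0 | 0 | 0% | 5.0% |
| 0.1 | 0.566 | 20% | 8.7% |
| 0.2 | 1.131 | 40% | 20.2% |
| 0.3 | 1.697 | 60% | 39.1% |

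If an item's SD were 2.5 points (also assumed), the last three rows would be shifts of 0.25, 0.5 and 0.75 points.

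True d = 0.50, shift favouring control, so the apparent effect is 0.50 − b:

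| b (SD) | Apparent effect (SD) | Power |
|---|---|---|
| 0 | 0.5 | 80.1% |
| 0.1 | 0.4 | 61.2% |
| 0.2 | 0.3 | 39.1% |
| 0.3 | 0.2 | 20.2% |

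**5. Which outcomes are exposed.** Participation, satisfaction and pain experience come from the APS-POQ-R handed back on the unit. PPQ items ask about knowledge and beliefs and leave less room for courtesy. Opioid use is taken from the medication administration record (Chart audits) and is not touched.

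**The case against.** The case on the other side is substantial.

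- **Same procedure in both arms.** Nurses on both units teach, complete education checklists and collect forms, and the in-services are not described as confined to the iPad unit. This stands: the shared part of any inflation cancels, and nothing in the documents demonstrates a differential part.
- **Details of the handover.** A reader might infer that patients pass an open form to the very nurse who taught them. The documents do not say so. The collector may be the charge nurse, nothing says that a nurse is present while the form is completed, and the collection protocol is in Appendix G, which is not in the supplied text. Limitations also allows that intervention-unit nurses may float to the control unit, so the two teams are not strictly separate.
- **Confidentiality rules exist.** Recruitment and Consent restricts data access to approved research personnel, and the Data Analysis Plan has the surveys go back to the researcher. Neither covers the moment of handover on the unit.
- **Patients are not explicitly told their arm.** This helps only in part, since the iPad is visible and the nurses know the arm in any case.
- **Bedside collection is a deliberate choice to protect response.** That is a fair reason, but sealed return on the unit keeps the benefit.
- **One unit per arm is the larger problem.** This is true. It affects every outcome however forms are returned, and envelopes do not cure it. The present point is only the part of it that runs through nurse collection.

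**Conclusion.** The point holds as a gap in procedure that is cheap to close. Unblinded unit nursing teams deliver the education and take back the ratings of it, no confidential return is described, and a between-unit reporting difference would be inseparable from the education effect on participation and pain experience.

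A reader might go further and conclude that the scores will be inflated in favour of the iPad and that this inflation is wholly confounded with arm. The documents do not support that. Only the part that differs between units reaches the contrast, and its existence, size and direction are unknown. The rejection rates of about 9%, 20% and 39% are arithmetic on assumed shifts of 0.1, 0.2 and 0.3 SD. They rest on a two-sided test, equal SDs, 64 per arm and no dropout; at zero shift the rate is 5%, and with a true effect a shift towards control would lower power instead. They show how sensitive the test would be and are not evidence of bias. If Appendix G already specifies confidential return, the main text need only say so.

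**What to change.** - **Return of forms.** In Data Collection Procedure and the matching text in Instruments, keep completion on the unit before discharge. Have the patient seal both forms in an envelope addressed to the researcher, then hand it back sealed or put it in a locked box. Use the identical procedure on both units.
- **Assurance on the form.** State that the nurses caring for the patient will not see the answers. A promise covering all unit staff could not be kept, because the plan gives staff RNs a part in data entry, checking and chart audit.
- **Data handling.** Have entry and checking done by the researcher, or by an approved RN who is not caring for that patient.
- **Limitations.** Add that residual unit-level differences in reporting cannot be separated from the education effect, since sealing the forms leaves other unit differences in place.

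The cost is envelopes and a line in the staff in-service. No extra staff are needed and the sample size is unchanged. The drawback is that nurses can no longer check for skipped items, so item-level missing data may rise slightly.
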